### **19.2. Anticipated Adverse Events**

The following anticipated adverse events (AE) have been reported due to suburethral sling placement, but are not limited to:

- Abscess
- Allergic reaction
- Bleeding
- Bruising/Hematoma
- Dehiscence of vaginal incision
- Detrusor Instability
- De Novo Dyspareunia
- Edema/Erythema
- Exposure
- Erosion
- Extrusion

- Fistula
- Hemorrhage
- Incontinence
- Infection
- Inflammation
- Irritation
- Migration of device from desired location
- Neuromuscular Events
- Ongoing pain (pelvic, vaginal, groin/thigh)
- Organ perforation
- Overactive bladder
- Pain
- Re-surgery
- Scarring/Scar contracture
- Urinary Retention
- Urinary Tract Obstruction
- Vessel/Nerve Injury
- Vaginal Discharge
- Sexual Dysfunction

#### 19.2.1. Mesh Exposure and Erosion Event Classification

Assessment of mesh exposure and/or erosion will occur at all follow-up visits post the 2 weeks telephone visit with physical exams performed at 6 weeks, 6, 12, 24, and 36 Months. Identification of mesh exposure and/or erosion will occur by the medical staff member performing the physical exam and will be documented as an adverse event on the Case Report Forms.

[REDACTED]

[REDACTED]

[REDACTED]

The classification of these events will be captured through eCRFs.

### **19.3. Risks associated with Participation in the Clinical Study**

There are no additional risks with participation in this clinical study outside of the anticipated risks (reference Section 19.2) for stress urinary incontinence as conducted according to standard of care procedures.

### **19.4. Risk Minimization Actions**

Additional risks may exist. Risks can be minimized through compliance with this protocol, performing procedures in the appropriate hospital environment, adherence to subject selection criteria, close monitoring of the subject's physiologic status during research procedures and/or follow-ups and by promptly supplying BSC with all pertinent information required by this protocol.

### **19.5. Anticipated Benefits**

Theoretical benefits of single-incision or transobturator mid-urethral slings may include reduction in incontinence episodes or resolution of symptoms via a minimally invasive surgical procedure.

## **20. Informed Consent**

Subject participation in this clinical study is voluntary. Informed Consent is required from all subjects or their legally authorized representative. The Investigator is responsible for ensuring that Informed Consent is obtained prior to performing any study-required procedures and/or testing, or data collection.

The obtaining and documentation of Informed Consent must be in accordance with the principles of the Declaration of Helsinki, ISO 14155, any applicable national regulations, and local Ethics Committee and/or Regulatory authority body, as applicable. The ICF must be approved by the center's IRB/EC, or central IRB, if applicable.

Boston Scientific will provide a study-specific template of the ICF to investigators participating in this study. The ICF template may be modified to meet the requirements of the investigative center's IRB/EC. Any modification requires approval from BSC prior to use of the form. The ICF must be in a language understandable to the subject and if needed, BSC will assist the center in obtaining a written consent translation. Translated consent forms must also have IRB/EC approval prior to their use. Privacy language shall be included in the body of the form or as a separate form as applicable.

The process of obtaining Informed Consent shall:

- be conducted by the Principal Investigator or designee authorized to conduct the process,
- include a description of all aspects of the clinical study that are relevant to the subject's decision to participate throughout the clinical study,
- avoid any coercion of or undue influence of subjects to participate,
- not waive or appear to waive subject's legal rights,
- use native language that is non-technical and understandable to the subject or his/her legal representative,
- provide ample time for the subject to consider participation and ask questions if necessary,
- ensure important new information is provided to new and existing subjects throughout the clinical study.

The ICF shall always be signed and personally dated by the subject or legal representative and by the investigator or an authorized designee responsible for conducting the informed consent process. If a legal representative signs, the subject shall be asked to provide informed consent for continued participation as soon as his/her medical condition allows. The original signed ICF will be retained by the center and a copy of the signed and dated document and any other written information must be given to the person signing the form.

Failure to obtain subject consent will be reported by BSC to the applicable regulatory body according to their requirements (e.g., FDA requirement is within 5 working days of learning of such an event). Any violations of the informed consent process must be reported as deviations to the sponsor and local regulatory authorities (e.g. IRB/EC), as appropriate.

If new information becomes available that can significantly affect a subject's future health and medical care, that information shall be provided to the affected subject(s) in written form via a revised ICF or, in some situations, enrolled subjects may be requested to sign and date an addendum to the ICF. In addition to new significant information during the course of a study, other situations may necessitate revision of the ICF, such as if there are amendments to the protocol, a change in Principal Investigator, administrative changes, or following annual review by the IRB/EC. The new version of the ICF must be approved by the IRB/EC. Boston Scientific approval is required if changes to the revised ICF are requested by the center's IRB/EC. The IRB/EC will determine the subject population to be re-consented.

A Screening/Enrollment Log will be maintained to document select information about candidates who fail to meet the general or “other specific” entry criteria.

## 21. Safety Reporting

### 21.1. Definitions and Classification

Adverse event definitions are provided in Table 21.1-1. Administrative edits were made to combine definitions from ISO 14155-2011 and MEDDEV 2.7/3 12/2010.

**Table 21.1-1: Adverse Event Definitions**

Term	Definition
Adverse Event (AE)  Ref: ISO 14155-2011  Ref: MEDDEV 2.7/3 12/2010	Any untoward medical occurrence, unintended disease or injury, or any untoward clinical signs (including an abnormal laboratory finding) in subjects, users or other persons, whether or not related to the investigational medical device.  NOTE 1: This includes events related to the investigational medical device or comparator.  NOTE 2: This definition includes events related to the procedures involved (any procedure in the clinical investigation plan).  NOTE 3: For users or other persons, this definition is restricted to events related to the investigational medical device.
Serious Adverse Event (SAE)  Ref: ISO 14155-2011  Ref: MEDDEV 2.7/3 12/2010	Adverse event that: 
 
• Led to death,
 
• Led to serious deterioration in the health of the subject, that either resulted in:               
 
○ a life-threatening illness or injury, or
 
○ a permanent impairment of a body structure or a body function, or
 
○ in-subject or prolonged hospitalization of existing hospitalization, or
 
○ medical or surgical intervention to prevent life-threatening illness or injury or permanent impairment to a body structure or a body function
 
 
 
• Led to fetal distress, fetal death, or a congenital abnormality or birth defect.
 
 NOTE 1: Planned hospitalization for a pre-existing condition, or a procedure required by the clinical investigational plan, without serious deterioration in health, is not considered a serious adverse event.
Device Deficiency  Ref: ISO 14155-2011  Ref: MEDDEV 2.7/3 12/2010	A device deficiency is any inadequacy of a medical device with respect to its identity, quality, durability, reliability, safety or performance.  NOTE 1: Device deficiencies include malfunctions, misuse or use errors, and inadequate labeling.

Abbreviations: EC=Ethics Committee; IRB=Institutional Review Board

Underlying diseases are not reported as AEs unless there is an increase in severity or frequency during the course of the investigation. Death should not be recorded as an AE, but should only be reflected as an outcome of a specific SAE (see Table 21.1-1 for AE definitions).

Any device related or study procedure related AE experienced by the study subject after informed consent, whether during or subsequent to the procedure, must be recorded in the CRF. Only device and procedure-related AE's are captured in this study.

Refer to Section 19 for the known risks associated with the study device(s).

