**Primary Statistical Hypothesis**

The single incision sling will be non-inferior to the standard outside-in transobturator sling for the treatment of female stress urinary incontinence in safety and effectiveness at 36 months as compared to Baseline.

Statistical testing will be performed to determine if success rate of improvement in stress urinary incontinence at 36 months of single incision sling (treatment) group will be non-inferior to transobturator device (control) group. The null hypothesis is that the success rate in treatment group is less than or equal to the success rate in control group minus margin:

$$H_0: \pi_{treatment} - \pi_{control} \leq -\Delta$$

The alternative hypothesis is:

$$H_a: \pi_{treatment} - \pi_{control} > -\Delta$$

where  $\pi_{treatment}$  and  $\pi_{control}$  are the success rate of improvement in stress urinary incontinence at 36 months in treatment group and control group respectively, and  $\Delta$  is defined as the non-inferiority margin.

**Postmarket Solyx™ Study PS120093: A Prospective, Non-Randomized, Parallel Cohort, Multi-center Study of the Solyx™ Single Incision Sling System vs. the Obtryx™ II Sling System for the Treatment of Women with Stress Urinary Incontinence**

Statistical Test Method	For each of the primary endpoint and serious adverse events, non-inferiority of the single-incision sling will be evaluated using a two-sided 90% confidence interval for the treatment difference (single-incision minus transobturator). The confidence interval will be calculated based on the pooling of treatment differences across propensity score strata. All statistical analyses will be performed by the Sponsor per the Statistical Analysis Plan. [REDACTED]
--------------------------------	---

[REDACTED]	[REDACTED]
------------	------------

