## 8.2. Treatment Assignment

This post-approval study is a non-randomized, prospective, parallel cohort study across multiple centers. Subjects will be screened against the study Inclusion/Exclusion criteria and if eligible, enrolled into the study after providing Informed Consent. Approximately 140 subjects will receive the Solyx Sling System as the treatment group, and 140 subjects will receive the Obtryx II Sling System as the control group across the entire study.

To reduce selection bias in this non-randomized study, each study center will be permitted to enroll subjects in only one of the treatment groups. Physicians will be selected based on device and clinical research experience and will decide which device to implant in subjects prior to study initiation at their center. This decision will be documented. All subjects meeting the eligibility criteria at the study center will be screened and enrolled, as applicable.

. Furthermore, at study completion and final data analysis, a comparison of baseline characteristics of patients in the two groups will occur and, if necessary, statistical adjustments performed to control for baseline differences.

Should one study-wide arm reach 140 subjects prior to the other, enrollment will be capped in that arm and the other study arm will remain open to enrollment until it also reaches 140 subjects. Those study centers enrolling the device arm that have met enrollment capacity will be closed, per Sponsor discretion.

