### 17.2. *Investigator Responsibilities*

The Principal Investigator of an investigational center is responsible for ensuring that the study is conducted in accordance with the Clinical Study Agreement, the investigational plan/protocol, ISO 14155, ethical principles that have their origins in the Declaration of Helsinki, any conditions of approval imposed by the reviewing IRB/EC, and prevailing local and/or country laws and/or regulations, whichever affords the greater protection to the subject.

The Principal Investigator's responsibilities include, but are not limited to, the following.

- Prior to beginning the study, sign the Investigator Agreement and Protocol Signature page documenting his/her agreement to conduct the study in accordance with the protocol.
- Provide his/her qualifications and experience to assume responsibility for the proper conduct of the study and that of key members of the center team through up-to-date curriculum vitae or other relevant documentation and disclose potential conflicts of interest, including financial, that may interfere with the conduct of the clinical study or interpretation of results.
- Make no changes in or deviate from this protocol, except to protect the life and physical well-being of a subject in an emergency; document and explain any deviation from the approved protocol that occurred during the course of the clinical investigation.
- Create and maintain source documents throughout the clinical study and ensure their availability with direct access during monitoring visits or audits; ensure that all clinical-investigation-related records are retained per requirements.
- Ensure the accuracy, completeness, legibility, and timeliness of the data reported to the sponsor in the CRFs and in all required reports.
- Record, report, and assess (seriousness and relationship to the device/procedure) every adverse event and observed device deficiency.
- Report to BSC, per the protocol requirements, all SAEs and device deficiencies that could have led to a SADE.

- Report to the IRB/EC and regulatory authorities any SAEs and device deficiencies that could have led to a SADE, if required by the national regulations or this protocol or by the IRB/EC, and supply BSC with any additional requested information related to the safety reporting of a particular event.
- Allow the sponsor to perform monitoring and auditing activities, and be accessible to the monitor and respond to questions during monitoring visits.

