**Table 21.4-1: Investigator Reporting Requirements**

[figure not shown]
Event Classification	Communication Method	Communication Timeline

Adverse device Effects and Serious Adverse Device Effects.
 
Events assessed for reporting shall include but are not limited to:
 
 
• Mesh exposure in the vagina
 
• Mesh erosion into the bladder
 
	
Complete AE CRF page with all available new and updated information
 
If requested by Boston Scientific provide all relevant source documentation (unidentified) for the reported event
	
 
• Within 2 business days of first becoming aware of the event or as per local/regional regulations.
 
• Reporting required through the end of the study
 
• When documentation is available
 

Adverse Events related to the study procedure for both surgical groups.
 
Events assessed for reporting shall include but are not limited to:
 
 
• Organ perforation
 
• Bleeding (including hemorrhage and hematoma)
 
• Pelvic pain
 
• Infection
 
• De novo dyspareunia
 
• Urinary retention
 
• Recurrent incontinence
 
• Other urinary problems
 
• Neuromuscular problems
 
• Revision/re-surgery
 
	
Complete the AE CRF page, which contains such information as onset date of the AE, treatment provided if any, resolution, assessment of seriousness, and relationship to study device.
	
 
• Within 2 business days of first becoming aware of the event or as per local/regional regulations.
 
• Reporting required through end of subject participation
 

Device Deficiencies (including but not limited to failures, malfunctions, and product nonconformities)
 
Note: Any Investigational Device Deficiency that might have led to a serious adverse event if a) suitable action had
	
Complete CRF with all available new and updated information
	
 
• Within 1 business day of first becoming aware of the event and as per local/regional regulations
 
• Reporting required through the end of the study
 

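### Related-only capture of adverse events in Protocol 21.1 conflicts with 17.2 and lets device-aware attribution decide which SAEs reach the non-inferiority comparison

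*Protocol*

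**What the plan says.** The synopsis (Statistical Test Method) says: "For each of the primary endpoint and serious adverse events, non-inferiority of the single-incision sling will be evaluated", using a two-sided 90% interval pooled over propensity strata. The visible sentence does not limit these events to related ones.

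The protocol then describes capture in different ways:

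- Table 21.1-1 defines an adverse event as any untoward occurrence, "whether or not related to the investigational medical device". An SAE is a subset of these.
- The text after that table says: "Only device and procedure-related AE's are captured in this study".
- The visible adverse-event rows of Table 21.4-1 are "Adverse device Effects and Serious Adverse Device Effects" and "Adverse Events related to the study procedure for both surgical groups". A further row covers device deficiencies.
- Section 17.2 requires the investigator to do this: "Record, report, and assess (seriousness and relationship to the device/procedure) every adverse event and observed device deficiency". The next bullet reads: "Report to BSC, per the protocol requirements, all SAEs and device deficiencies that could have led to a SADE".

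Under 21.2 and 21.3 the investigator judges the relationship to device and procedure, and both classification tables keep an unrelated class. Under 8.2, "each study center will be permitted to enroll subjects in only one of the treatment groups", and the physician chooses the device before the center opens. SAP 5.2 itself says that treatment arm and center are confounded.

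**The concern.** One site cannot satisfy both the 21.1 sentence and the 17.2 bullet on every adverse event. For non-serious events that would be a drafting matter. For SAEs it touches a tested outcome.

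The main issue is what happens if 21.1 governs. The relatedness call then decides whether an SAE exists in the data at all. It is made by someone who chose the device and implants only that device in the study. If Solyx and Obtryx investigators attribute differently, captured SAE rates differ even when true rates do not. The propensity score uses baseline data only (Protocol 12.2.2, SAP 4.2), so it cannot adjust for a process that acts after surgery. A later reviewer cannot re-examine events that were never captured, short of retrospective source review. Deaths are a partial exception, because 11.7 puts them on the CRF whatever the cause.

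A secondary issue is that centers might follow different rules. With one device per center, that could become a difference between arms, but only under a further condition examined below.

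**Working it through.** **The passages side by side.**

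| Place | Non-serious AE, unrelated | SAE, unrelated |
|---|---|---|
| 21.1 text | not captured | not captured |
| Table 21.4-1, visible rows | not listed | not listed |
| 17.2, every-adverse-event bullet | record and report | record and report |
| 17.2, SAE bullet | not addressed | report, per the protocol requirements |

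The qualifier in the SAE bullet can be read as deferring to section 21. The bullet above it has no qualifier, so the conflict remains. No visible text says which rule governs.

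**Inputs.** From the documents: 140 subjects per arm; a two-sided 90% interval, so z = 1.645; difference taken as Solyx minus Obtryx. No SAE rate, attribution share or SAE margin is visible, so all of these are assumed, and there is no stated SAE figure to reproduce. The calculation is an unstratified Wald approximation with equal true SAE risk in both arms.

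**Formulas.** Captured risk = true risk × share called related. SE = √[p₁(1−p₁)/140 + p₂(1−p₂)/140]. Chance of concluding non-inferiority at margin M = Φ((M − d)/SE − 1.645), where d is the captured difference.

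**Attribution route.**

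- Small gap: 5% risk, 70% vs 60% called related. Captured 0.05 × 0.70 = 3.5% and 0.05 × 0.60 = 3.0%; d = 0.5 points; SE 2.12; half-width 1.645 × 2.12 = 3.5 points.
- Large gap: 10% risk, 80% vs 50% called related. Captured 8% and 5%; d = 3 points; SE 2.94; half-width 4.8 points.

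Chance of concluding SAE non-inferiority:

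| Case | Assumed margin | Solyx centers capture more | Equal capture | Solyx centers capture less |
|---|---|---|---|---|
| Small gap | 5 points | 68% | 76% | 83% |
| Small gap | 10 points | 99.8% | 99.9% | 99.95% |
| Large gap | 5 points | 17% | 52% | 86% |
| Large gap | 10 points | 77% | 96% | 99.7% |
| Large gap | 15 points | 99.3% | 99.97% | near 100% |

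Equal capture is taken at the mean of the two captured rates (3.25% and 6.5%).

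**Mixed-rule route, only if unrelated SAEs are counted wherever they arrive.** Shift = risk × share called unrelated × gap between arms in the share of subjects at centers following 17.2.

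- Low: 0.05 × 0.20 × 0.25 = 0.25 points.
- Middle: 0.10 × 0.35 × 0.50 = 1.75 points. Captured rates are 6.5% + 3.5% × 0.75 = 9.125% and 6.5% + 3.5% × 0.25 = 7.375%; half-width 5.4 points. The chance is 26% vs 45% with equal capture at a 5-point margin, 81% vs 92% at 10 points, and 99.2% vs 99.8% at 15 points.
- Extreme: 0.10 × 0.50 × 1.00 = 5 points.

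If only related SAEs are analysed, this route contributes nothing.

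**The case against.** A reader might infer that the SAE result depends on which reporting rule each center follows. The documents do not support that as stated. A center following 17.2 must also assess relationship, and 21.2, 21.3 and the AE form described in Table 21.4-1 ask for attribution. Unrelated events would arrive labelled, and a related-only analysis could drop them. This objection stands, and it makes mixed rule-following secondary.

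The SAE definition and margin may sit in redacted text, and the endpoint may be limited to related SAEs. Visible numbering also runs from 21.4 to 21.6 and then to section 23, so event review in unseen text cannot be excluded. That too stands. However, a related-only endpoint would still rest on investigator attribution, and a review could not see events that were never captured.

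The classification thresholds are inclusive. A device event counts as related even if another cause is equally likely, and a procedure event is possibly related on timing alone. This narrows discretion and makes the 80% vs 50% case a severe one. It does not remove discretion, and 21.1 does not say whether possibly related counts as related.

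Every rate and margin above is assumed. The only visible margin is 15 points, for effectiveness, and at 15 points the effect is small. At 5 points the 1.75-point and 3-point cases succeed only 45% to 52% of the time even with equal capture, so part of the drop reflects low power at that margin. Nor is a simple proportion at 140 per arm established: Protocol 12.2.1 and SAP 4.6 use available cases, the synopsis assumes 20% loss, and SAP 4.6 mentions Kaplan-Meier estimates. These points limit the size of the concern but not its mechanism.

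Finally, related-only capture is an openly stated choice in a post-market study, and trimming the 17.2 bullet would also remove the contradiction. That is true, but it would leave a tested safety outcome with no all-cause check.

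**Conclusion.** The contradiction between 17.2 and 21.1 is real and lies in current text, and the passages must be reconciled. The statistical consequence is narrower. If 21.1 governs, device-aware attribution determines which SAEs exist in the data, baseline propensity stratification cannot correct it, and SAEs judged unrelated are unavailable for checking.

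A reader might go further and conclude that the SAE comparison is biased, or biased in favour of Solyx. The documents do not show this. If investigators attribute alike and one rule is followed, there is no distortion. If they do not, it could run either way. On the assumed rates, the attribution shift is 0.5 to 3 points: negligible with a small gap and a wide margin, material with a large gap and a tight margin. The primary effectiveness comparison is not touched. The amendment is worth making, with medium confidence, because uncaptured events cannot readily be recovered later.

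**What to change.** 1. Amend 21.1 and Table 21.4-1 to agree with 17.2 for SAEs: every SAE is recorded with its device and procedure attribution and sent to the sponsor.
2. Keep related-only capture for non-serious events, and amend the every-adverse-event bullet in 17.2 to match.
3. Report the SAE comparison for all-cause and for related SAEs, with whichever the endpoint text (not visible here) specifies as the main one. The all-cause result does not pass through the attribution filter. The related result still does, and the investigator still judges seriousness in both.

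Cost: a protocol and CRF-instruction amendment, plus some extra SAE records. Subjects with an added unrelated SAE = 280 × all-cause risk × share called unrelated (assumed 20% to 50%): 2.8 to 7 at 5% risk, 5.6 to 14 at 10%, 11.2 to 28 at 20%. At an assumed 1.5 events per such subject, the 10% case gives about 8 to 21 records. Unrelated events add some noise to the all-cause comparison; the related-SAE analysis beside it covers this.
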